THE IRB MUST BE NOTIFIED OF COMPLETION OF THIS STUDY.....	32

REFERENCES	33
TABLES.....	34
TIMELINE AND EVENTS SCHEDULE.....	34
STUDY SCALES AND ASSESSMENTS.....	35

INVESTIGATOR'S STATEMENT OF AGREEMENT

I have read the foregoing protocol and agree that it contains all necessary details for conducting the study. I will conduct the study as outlined herein and will complete the study within the time designated.

I agree to conduct this protocol in accordance with local regulations, external standards and applicable ICH and Good Clinical Practice (GCP) guidelines.

I will provide copies of the protocol, including any amendments, and all pertinent information to all individuals responsible to me who assist in the conduct of this study. I will discuss this material with them to ensure they are fully informed regarding the ZELTIQ Aesthetics, Inc. device and the conduct of the study.

I further agree to provide access to ZELTIQ Aesthetics Inc, its designees, or regulatory authorities to any source documents from which case report form information may have been generated.

I agree to maintain the confidentiality of all information received or developed in connection with this protocol.

Principal Investigator
(Print name)

Principal Investigator
(Principal Investigator's signature)

Date

[figure not shown]
CLINICAL SITE

STUDY SYNOPSIS

Purpose	The purpose of this single-site clinical study is to evaluate the safety and effectiveness of three (3) treatments sessions with the ZELTIQ Aesthetics, Inc. Rapid Acoustic Pulse (RAP) device for the improvement in the appearance of cellulite.
Primary Effectiveness Objective	
 • RAP treatment effectiveness: The primary effectiveness objective will demonstrate improvement in the appearance of cellulite as determined by correct identification of baseline vs 12-weeks post final treatment images [REDACTED] [REDACTED] by at least 2 of 3 blinded independent physician reviewers (IPR).
Primary Safety Objective	
 • RAP treatment safety: The primary safety objective is to evaluate the safety of the RAP (Rapid Acoustic Pulse) device for cellulite treatments through the monitoring of the incidence of adverse events (AEs) and adverse device effects (ADEs); serious adverse events (SAEs) and SADEs (serious adverse device effects) and pain assessments.

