Secondary Effectiveness Objective	
 • RAP treatment effectiveness: The secondary effectiveness objective is to demonstrate the improvement in the appearance of cellulite as determined by the study participants selecting “Agree” or “Strongly Agree” as answers to the Participant Satisfaction Survey (Assessment 3): when comparing side-by-side before and after photographs.
Test Device	ZELTIQ Aesthetics, Inc. Rapid Acoustic Pulse (RAP) device.
Treatment	
Each cellulite treatment session will consist of RAP treatment [REDACTED] to bilateral thigh and/or buttock areas using the same treatment settings for both sides.
 
The participants will have three (3) separate cellulite treatment sessions. The second treatment session will occur four (4) weeks post the initial treatment. The third treatment session will occur twelve (12) weeks post the second treatment.

Control	For each cellulite treatment area, the pre-treatment photos of the thighs and/or buttocks area will serve as a control.
Study Design	Non-significant risk, single-site, prospective clinical trial.
Planned Number of Sites / Countries	One clinical trial site located in the United States.

Planned Duration of Participant Engagement	Up to seventy-two (72) weeks [REDACTED]
Planned Number of Participants/ Treatment Areas	Up to 15 participants [REDACTED] (total of two thighs and/or buttocks per participant) The clinical site (CS) will recruit up to 15 participants. This will provide a total of up to thirty treatment areas.
Primary Effectiveness Endpoint	
 Effectiveness Endpoint: An Independent Photo Review (IPR) panel will be asked to identify the 12-weeks post final treatment photographs from randomly placed side-by-side before and after photographs, for all participants who meet all the inclusion criteria and none of the exclusion criteria and complete the 12-weeks follow-up visit. The number of before and after photos correctly identified by at least 2 of 3 blinded reviewers from the IPR panel will be recorded. [REDACTED]
Primary Safety Endpoint	
 RAP treatment safety endpoint: To demonstrate safety through the absence of unexpected adverse events (UAEs) and serious adverse events (SAEs) directly attributable to the RAP device or treatments.

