	
 • Metal or plastic implants (vascular stent, or implants in the hips, knees, etc.) in the treatment areas. • Active electronic implants such as pacemakers and defibrillators. • History of coagulopathy and/or on anticoagulant medication. • Skin disorders (skin infections or rashes, psoriasis, etc.) in the treatment areas. • Medical disorder that would hinder wound healing or immune response. • Any surgical procedure in the treatment areas in the prior 3 months or planned during the duration of the study. • Any other condition/disease/situation which, as deemed by the PI, would preclude participant from safely participating in or completing the study visits or that may confound study results.
--	---

INTRODUCTION

Overview

The Rapid Acoustic Pulse (RAP) is an electrohydraulic (EH) device designed to improve the appearance of cellulite. Devices using RAP technology have been successfully used in seven human clinical trials to accelerate laser-based tattoo removal, a proof of concept (POC) and pivotal clinical trials to improve the appearance of cellulite without the occurrence of device related UAEs or SAEs. The purpose of this single-site, multi-treatment clinical study is to evaluate the safety and effectiveness of ZELTIQ Aesthetics, Inc.’s Rapid Acoustic Pulse (RAP) device for the improvement of cellulite.

Cellulite

Cellulite is the often aesthetically displeasing rippling or dimpling of the skin most commonly located on the thighs and buttocks of women. Its appearance and texture are often likened by laypeople to that of “cottage cheese” or an orange peel [1].

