Both thighs in five participants (10 treatment areas) having Grade II cellulite, were treated with the RAP device with [REDACTED] pulse rate. On one site, a single RAP treatment was provided. On the other site, a RAP treatment was given every three weeks for a total of three RAP treatments. Immediately after each RAP treatment, the treated areas were assessed for AEs. Additionally, the participants were asked about discomfort from the procedure. Finally, photographs of the treatment areas taken prior to, and at 12-weeks post the first treatment, were assessed to determine if the RAP treatment had the effect of improvement in the appearance of cellulite.

Results indicated there were no safety or discomfort issues resulting from the RAP treatments. Mild redness around hair follicles, which resolved within hours was the only side effect. There were no reports of erythema, swelling or bruising. [REDACTED]

Safety Conclusion

[figure not shown]
Given the safety and tolerability results of the Acoustic Wave Device (AWD) in the POC cellulite human clinical trial, the RAP device is anticipated to be safe and tolerable when used in this clinical trial. The RAP device that will be used in this study uses the same Rapid Acoustic Pulse technology that is the basis for ZELTIQ Aesthetics, Inc.'s AWD (Acoustic Wave Device) and RAP devices in earlier trials.

Pivotal Study of Safety and Efficacy of RAP Cellulite Clinical Trial

A multi-center, pivotal study was conducted to assess the safety and efficacy of the ZELTIQ Aesthetics, Inc. RAP device for the temporary improvement of cellulite on the treatment areas of thighs and/or buttocks. Sixty-seven participants enrolled in the study. Treatments were conducted at [REDACTED] Efficacy was documented at 12- weeks post treatment. No SAE or device related unexpected or SAE occurred during the study.

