Short-term (12-week) analysis was conducted in fifty-six participants who completed a full treatment of the identified treatment areas and who completed the 12-week follow up visit. Serial clinical photographs were collected before RAP treatment under standardized conditions at the baseline (0-week) visit and at the short-term (12-week) follow-up visits. Photographs were assessed by blinded independent reviewers (IPR) to correctly identify the 12-weeks post-treatment photographs from randomly placed side-by-side comparison of before and after photographs. Additionally, the IPR graded the pre-treatment and post-treatment images using the simplified 6-point Cellulite Severity Scale (CSS) [3] and improvement using the Global Aesthetic Improvement Scale (GAIS). Safety assessments included evaluation of Adverse Events (AEs) via physician examination during and after the treatment.

[figure not shown]
The short-term (12-week) results demonstrated that a single non-invasive acoustic subcision session can safely provide meaningful improvement in the appearance of cellulite in terms of depressions with minimal treatment pain and no post-treatment down time. The post-treatment photographs were correctly identified by blinded IPR from randomized pairs of pre/post-treatment photographs at a rate of 96.4%. Furthermore, the participants had a mean CSS reduction of 1.01 (a 29.5% reduction from baseline). Cellulite was graded as improved, much improved, or very much improved using the GAIS at 90.9% of treated locations. Finally, 92.9% of participants reported positive satisfaction responses. No device related unexpected or serious AEs were noted at treatment or follow-up. Overall average pain score during treatment was 2.4 (0-10 pain scale) and 0.3 immediately post-treatment.

[figure not shown]

Protocol 2021-06 Study Objectives and Endpoints

Primary Objectives	Primary Outcome Endpoints
RAP treatment effectiveness: The primary objective is to demonstrate improvement in the appearance of cellulite by blinded independent physician reviewers (IPR).	Effectiveness Endpoint: An IPR panel will be asked to identify the 12-weeks post final treatment photographs from randomly placed side-by-side before and after photographs, for all participants who meet the all inclusion criteria and none of the

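### The synopsis words primary safety as demonstrated by an absence of events; the rest of the plan is descriptive, and zero events in at most 15 people cannot demonstrate safety

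*Combined protocol and SAP*

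**What the plan says.** The Primary Safety Endpoint row of the Study Synopsis states the endpoint as "To demonstrate safety through the absence of unexpected adverse events (UAEs) and serious adverse events (SAEs) directly attributable to the RAP device or treatments". It gives no threshold, confidence level or decision rule.

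Three other places describe primary safety differently:

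- **Study Synopsis, Primary Safety Objective.** The stated aim reads "evaluate the safety of the RAP (Rapid Acoustic Pulse) device for cellulite treatments through the monitoring of the incidence of adverse events (AEs"; the same sentence goes on to ADEs, SAEs, SADEs and pain assessments.
- **Study Objectives and Endpoints table.** Counts and proportions of participants are summarised for AEs, SAEs, ADEs, SADEs and unanticipated events. The monitoring objective, including pain, is repeated.
- **Study Results/Analysis, Safety Analysis.** Incidence and severity are tabulated, with a full listing. The Safety Analysis Set is everyone enrolled in whom RAP treatment was at least started.

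Sample Size Determination sets enrolment at up to 15, on exploratory grounds and without a power calculation. On the regimen, the synopsis says: "The participants will have three (3) separate cellulite treatment sessions".

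On earlier experience, the Introduction cites tattoo-removal trials and the cellulite trials "without the occurrence of device related UAEs or SAEs". The pivotal study enrolled 67 participants, of whom 56 were analysed at 12 weeks. It reports no device-related unexpected or serious event and concludes that "a single non-invasive acoustic subcision session can safely provide meaningful improvement".

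**The concern.** The plan carries two versions of its primary safety endpoint. They differ in form, because one is a demonstration and the other a summary. They also differ in scope: the synopsis row counts only attributable unexpected events and SAEs, while the other places cover all AEs and device effects, with pain or severity added.

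The safety tables would look much the same under either version. What changes is the conclusion and the events it rests on. A report that follows the synopsis row could turn a zero count into a statement that the three-session regimen has been shown to be safe. A report that follows the endpoints table would give the counts without that statement. The Introduction already cites the absence of device-related events in earlier trials as support, so the same step could easily be taken here.

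**Working it through.** **No figure to reproduce.** The visible text gives no acceptable event rate, safety bound or confidence level. The 95% level and the true rates below are assumptions.

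**Inputs.** n is at most 15, with no stated minimum (Sample Size Determination). The denominator is the Safety Analysis Set. The outcome is at least one qualifying event per participant.

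**Step 1: what zero events would exclude.** The exact (Clopper-Pearson) upper limit for 0 of n is 1 − 0.05^(1/n) one-sided and 1 − 0.025^(1/n) for a two-sided 95% interval.

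| n | One-sided | Two-sided |
|---|---|---|
| 15 (the maximum) | 1 − 0.05^(1/15) = 18.1% | 1 − 0.025^(1/15) = 21.8% |
| 10 (if enrolment falls short; assumed) | 25.9% | 30.8% |

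Even at full enrolment, a per-participant risk just under 18% (one-sided) or 22% (two-sided) could not be excluded.

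**Step 2: how easily the synopsis wording would be met.** The chance of zero events in 15 is (1 − p)^15.

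| True risk p | Chance of zero events in 15 |
|---|---|
| 1% | 86.0% |
| 2% | 73.9% |
| 5% | 0.95^15 = 46.3% |
| 10% | 0.90^15 = 20.6% |
| 15% | 8.7% |

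A device with a 10% risk would meet the wording about one time in five, and one with a 5% risk nearly half the time.

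**Step 3: scale.** With zero events, the one-sided 95% limit falls below 10% only from 29 participants (ln 0.05 / ln 0.90 = 28.4, rounded up) and below 5% only from 59 (ln 0.05 / ln 0.95 = 58.4, rounded up). These figures show the distance from a demonstration. They are not a proposal to enlarge the trial.

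**Step 4: what earlier trials add.** By the two-sided formula, zero events gives 1 − 0.025^(1/67) = 5.4% for all 67 enrolled in the pivotal study, or 1 − 0.025^(1/56) = 6.4% for the 56 analysed. That is useful for a single session, which is what the pivotal results describe. Three treatments were given only in the proof-of-concept study: "Both thighs in five participants (10 treatment areas) having Grade II cellulite" were treated, and "On the other site, a RAP treatment was given every three weeks for a total of three RAP treatments". That is one side in five people, at a different spacing from this trial. The tattoo-removal trials concern another use, and no participant counts are given for them.

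**The case against.** The strongest reply is that this is one loosely worded row. The analysis section governs what is tabulated and is descriptive, the sample is declared exploratory, and no test or success rule hangs on the row. All of that is true, and it limits the size of the problem. It does not remove it: the row is labelled as the primary safety endpoint, and its wording invites a conclusion that the other sections do not.

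Exact intervals can also be called a preference in a descriptive study. Nothing in the documents requires them, but a bare zero on so small a denominator is easily over-read.

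A reader might infer more than the documents support in four ways:

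- **That the plan has a formal pass/fail safety test, or that the trial must be larger.** The visible text contains no such test, and an exploratory sample is acceptable for description.
- **That the limit should be computed in those who received all three sessions.** Participant Withdrawal and Early Termination allows withdrawal for safety, and the adverse event section records treatment discontinuation as a possible impact. Someone who stops because of an event would leave that group, so its rate could understate the risk of the planned regimen.
- **That prior experience is almost nil.** Quoting only the five-person proof-of-concept study would be selective, because the pivotal study gives sizeable single-session data. The protocol itself says only that it anticipates the device to be safe.
- **That the mix of unexpected and unanticipated, which the adverse event section does not define, is an error in itself.** It is missing detail with little effect, since all reports are to be listed.

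**Conclusion.** The point holds as an inconsistency with a consequence for the conclusion, not for the counts. The synopsis row departs from the objective, the endpoints table and the safety analysis in both form and scope, and an absence of events in at most 15 people cannot carry the claim it makes. At an assumed 95% level the best case, 0/15, is compatible with a per-participant risk of up to 18.1% (one-sided) or 21.8% (two-sided), and fewer participants would widen this. Because the plan names no acceptable rate, the finding is that rates below those limits cannot be excluded. It is not a finding that the device is unsafe. The pivotal data narrow the uncertainty for one session and do not cover three. The row should be corrected; nothing here calls for a change to the design.

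**What to change.** 1. Replace the synopsis Primary Safety Endpoint with the descriptive endpoint from the Study Objectives and Endpoints table, and drop the wording about demonstrating safety by absence.
2. In the full Safety Analysis Set, report the number and proportion of participants with attributable unexpected or unanticipated events, and with SAEs. Give each an exact two-sided 95% interval and show the upper limit when the count is zero. State which of the protocol's causality categories were counted as attributable.
3. Report descriptively how many participants received one, two and three sessions, with the reasons for stopping. Do not base a safety interval on three-session completers alone.

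**Cost.** One synopsis row is reworded, intervals are added for two kinds of event, and a short table of sessions received is added. Sample size, visits and data collection stay as they are. The real downside for the sponsor is a less favourable safety statement, with a wide interval even if no event occurs.

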Secondary Effectiveness Endpoint	
 Effectiveness Endpoint: For all participants who meet all inclusion criteria and none of the exclusion criteria and are followed up at the 12-week timepoint post final treatment, [REDACTED] he study participants select “Agree” or “Strongly Agree” to the Participant Satisfaction Survey (Assessment 3): [REDACTED]
[REDACTED]	

Inclusion Criteria	
 • Healthy candidates ages 18-50 years. • Seeking treatment of cellulite in the thigh and/or buttock areas. • Areas of moderate to severe cellulite on bilateral thigh and/or buttock using the Cellulite Dimple – At Rest Scale at Baseline with grades of 2 or 3 based on review of photos taken under the same lightening conditions planned for the trial. • Participant will not have had minimally invasive, invasive, or energy-based cellulite (liposuction, subcision, RF, laser, ESWT, cryo-lipolysis, muscle stimulation, etc.) treatments in the treatment areas in the prior 12 months. • Participant will not have used topical based cellulite treatments for prior 3 months and will not use during the trial. • Participant will not have used spray-on tanning treatments for 3 months prior to or during the term of the trial. • Participant must be able to provide written informed consent, understand and is willing to comply with all study-related procedures and follow-up visits.
Exclusion Criteria	
 • Participant is unwilling to have research photos and/or videos taken of treatment areas in the presence of or by Sponsor's research team. • Participant is unwilling to have RAP treatment provided in the presence of Sponsor's research team. • Participant is pregnant or planning to become pregnant during the duration of the study. • Participant is unwilling to commit to follow-up visits.

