Participants who meet all inclusion criteria and none of the exclusion criteria will be enrolled in the study and assigned a participant No./ID in sequential order (i.e., 01, 02, 03, etc.)

[figure not shown]
Inclusion Criteria

- Healthy candidates ages 18-50 years
- Seeking treatment of cellulite in the thigh and/or buttock areas
- Areas of moderate to severe cellulite on bilateral thigh and/or buttock using the Cellulite Dimple – At Rest Scale at Baseline with grades of 2 or 3 based on review of photos taken under the same lightening conditions planned for the trial.
- Participant will not have had minimally invasive, invasive or energy-based cellulite (liposuction, subcision, RF, laser, ESWT, cryo-lipolysis, muscle stimulation, etc.) treatments in the treatment areas in the prior 12 months.
- Participant will not have used topical based cellulite treatments for prior 3 months and will not use during the trial.
- Participant will not have used spray-on tanning treatments for 3 months prior to or during the term of the trial.
- Participant must be able to provide written informed consent, understand and is willing to comply with all study-related procedures and follow-up visits.

Exclusion Criteria

- Participant is unwilling to have research photos and/or videos taken of treatment areas in the presence of Sponsor's research team.
- Participant is unwilling to have RAP treatment provided in the presence of Sponsor's research team.
- Participant is pregnant or planning to become pregnant during the duration of the study.
- Participant is unwilling to commit to follow-up visits.

- Metal or plastic implants (vascular stent, or implants in the hips, knees, etc.) in the treatment areas.
- Active electronic implants such as pacemakers or defibrillators.
- History of coagulopathy and/or on anticoagulant medication.
- Skin disorders (skin infections or rashes, psoriasis, etc.) in the treatment areas.
- Medical disorder that would hinder wound healing or immune response
- Any surgical procedure in the treatment areas in the prior 3 months or planned during the duration of the study.
- Any other condition/disease/situation which, as deemed by the PI, would preclude participant from safely participating in or completing the study visits or that may confound study results.

STUDY PROCEDURES

Study procedures as described in this section are outlined in the schedule of assessments.

Study Visits

Visit 1 Baseline Screening and Consent Form (Day -30 to Day 0)

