- Review study procedures, assessments and visit schedule with participants
- [REDACTED]
- Obtain informed consent
- Review of Inclusion/Exclusion criteria
- [REDACTED]
- Fitzpatrick Skin Type Scale (Scale 2)
- [REDACTED]
- Demographics and baseline characteristics (including weight and height)
- Limited physical exam, blood pressure and heart rate
- Review of medical history (3-year history)
- Urine pregnancy test for women of childbearing potential
- Concomitant medication
- 2D Photos of the treatment area
- [REDACTED]

Visit 2 Treatment

Pre-treatment Activities

- Review concomitant medication
- Take vital signs
- Urine pregnancy test for women of childbearing potential
- Adverse event evaluation
- Confirm eligibility
- [REDACTED]
- 2D Photos of the treatment area taken pre and post marking
- [REDACTED]

Note: Visits 1 and 2 may be combined if feasible at time of screening and enrollment.

Treatment

- Administer treatment in accordance with Treatment Recommendations (**See Appendix A, Treatment Recommendations**)

Immediate Post-Treatment Activities

- Adverse event evaluation

Visit 3 Follow Up Visit 4-Weeks Post 1st Treatment (+/- 14 days) and 2nd Treatment

Pre-treatment Activities

- Review concomitant medication
- Take vital signs
- Weight
- Urine pregnancy test for women of childbearing potential
- Adverse event evaluation
- Confirm eligibility
- Collect Diary – Treatment 1
- [REDACTED]
- 2D Photos of the treatment area taken pre and post marking

Treatment

- Administer treatment [REDACTED]

Immediate Post-Treatment Activities

- Adverse event evaluation [REDACTED]

Visit 4 Follow Up Visit 12-Weeks Post 2nd Treatment (+/- 14 days) and 3rd Treatment

- Review concomitant medication
- Take vital signs
- Weight
- Urine pregnancy test for women of childbearing potential
- Adverse event evaluation
- Confirm eligibility
- [REDACTED]
- [REDACTED]
- 2D Photos of the treatment area taken pre and post marking [REDACTED]

Treatment

[figure not shown]
- Administer treatment in accordance with Treatment Recommendations (See Appendix A, Treatment Recommendations)

Immediate Post-Treatment Activities

[figure not shown]
- Adverse event evaluation [REDACTED]

Visit 5 Follow Up Visit 12- Weeks Post 3rd Treatment (+/- 14 days)

[figure not shown]
- Weight
- Review concomitant medication
- Adverse Event evaluation
- [REDACTED]
- 2D Photos of the treatment area

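### The visible plan does not say which pre-treatment photo is the control; if it is the eligibility photo, regression to the mean can lift correct identification above 50% without any treatment effect.

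*Combined protocol and SAP*

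**What the plan says.** **Selection.** The Inclusion Criteria (Study Synopsis and Selection of Study Population) admit bilateral cellulite graded "using the Cellulite Dimple – At Rest Scale at Baseline with grades of 2 or 3 based on review of photos", the photos being "taken under the same lightening conditions planned for the trial". The Full Analysis Set requires every inclusion criterion to be met, so this selection carries into the primary analysis.

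**Control.** There is no untreated or sham area. In the Synopsis, Control row, "the pre-treatment photos of the thighs and/or buttocks area will serve as a control".

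**Primary comparison.** The Primary Effectiveness Objective rests on "correct identification of baseline vs 12-weeks post final treatment images". Reviewers see "randomly placed side-by-side before and after photographs", and "The number of before and after photos correctly identified by at least 2 of 3 blinded reviewers from the IPR panel will be recorded". The secondary endpoint also has participants judge the 12-week photo against the pre-treatment photo.

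**Photo occasions before treatment.** There are two. The first is the visit headed "Visit 1 Baseline Screening and Consent Form (Day -30 to Day 0", which lists 2D photos. The second is Visit 2, whose pre-treatment list includes "2D Photos of the treatment area taken pre and post marking" and also a re-check of eligibility. A note there and under Table 1 allows Visits 1 and 2 to be combined.

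**What cannot be seen.** No visible text says which of these images is shown to the panel or to participants. Parts of the objective, the endpoint and the visit lists are redacted.

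**The concern.** The plan uses one label, baseline, for the photo that qualifies a participant, for the first visit and for the image compared with the 12-week photo. The natural reading is that the eligibility photo also serves as the control. When Visits 1 and 2 are combined, the two at least come from the same occasion.

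That matters because a person admitted when one image looked severe enough will on average look somewhat milder in any later image, to the extent that appearance varies between occasions. Random left-right placement and blinding do not remove this, because the difference is in the images and not in what the reviewers know. With no concurrent control, the shift would be read as a device effect, both in the panel's identifications and in the participants' side-by-side ratings. A study of up to 15 participants has little room to absorb such a shift when the result is modest.

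**Working it through.** **No plan figure to reproduce.** The sample size is stated to be practical and exploratory, and no null rate, alpha, power or photo repeatability is visible.

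**Chance level.** If the images cannot be told apart and the three reviewers guess independently, a majority is correct with probability 3 × 0.5³ + 0.5³ = 0.50.

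**Zero-effect model.** Let X be the severity of the eligibility photo and Y that of the later photo. Both are standard normal with correlation r (photo-to-photo reliability), and there is no treatment effect. A participant enters if X > c, and the reader calls the milder image the after image. Given X = x, Y has mean rx and variance 1 − r², so

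P(Y < x) = Φ(kx), with k = √((1 − r)/(1 + r)).

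The expected correct rate is the average of Φ(kX) over X > c. At a median cut-off (c = 0) this is 0.5 + arctan(k)/π. For r = 0.8, k = √(0.2/1.8) = 0.333, arctan(k) = 0.322, and the rate is 0.5 + 0.322/3.1416 = 0.602.

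**Assumptions.** The documents give neither r nor the share of candidates screened out, so both are varied:

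| Reliability r | 10% excluded | 25% excluded | 50% excluded | 69% excluded |
|---|---|---|---|---|
| 0.60 | 0.534 | 0.577 | 0.648 | 0.709 |
| 0.70 | 0.530 | 0.566 | 0.627 | 0.679 |
| 0.80 | 0.524 | 0.554 | 0.602 | 0.645 |
| 0.90 | 0.517 | 0.538 | 0.572 | 0.602 |
| 0.95 | 0.512 | 0.527 | 0.550 | 0.572 |

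The range is about 51% to 71%. A simulation of the 2-of-3 rule with reader noise (SD 0.3) barely changes it: 0.598 instead of 0.602 at r = 0.8 and a median cut-off.

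**Sensitivity of the conclusion.**
- Separate pre-treatment photo, not used for selection: 0.50 at every setting. That photo and the later one stand in the same relation to the selection.
- Only the screening grader's reading is noisy and the image itself is stable: 0.50. Grading error does not carry over to a different panel looking at the image.
- Grades above 3 exist and are excluded (r from 0.5 to 0.9, several selection bands): 0.458 to 0.640, so the shift can vanish or reverse.
- Most extreme setting tried (r = 0.5, 75% excluded): 0.755.

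**Scale of the consequence.** As a yardstick only, take the smallest counts whose upper tail at 0.50 is at most 5%: 12 of 15 and 20 of 30. If the true rate were 0.60 with no device effect, at least 12 of 15 would occur with probability 9.1% (1.8% at 0.50), and at least 20 of 30 with probability 29.1% (4.9% at 0.50). The second figure treats the two sides of a participant as independent, which is a simplification.

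**The case against.** The strongest reply is that the documents never equate the two images. The Control row refers to pre-treatment photos in general, and Visit 2 supplies a second set before the first session. Text next to the objective, the endpoint and the visit lists is blacked out, so the choice may already be specified there. A reader might infer that the plan, as written, uses the selection photo as its control; the visible text does not establish that. This part of the objection stands, and the point is therefore conditional.

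A reader might also infer that regression to the mean by itself must push the rate above chance. That is too strong. It needs variation in the images themselves, and the plan limits some of it: the scale is graded at rest, and lighting and equipment settings are standardized for baseline photographs. Variation is not excluded, however. The Cellulite section itself links dimpling to weight gain and water absorption, and no visible text fixes stance.

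Candidates already seek cellulite treatment, so the grade criterion may screen out few of them. The 10% column then applies, and the excess is 1 to 3 percentage points.

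Finally, the analysis is descriptive and the study exploratory, with no visible test against 50%. That limits the consequence but does not remove it, because the stated aim is to demonstrate improvement.

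**Conclusion.** The concern holds in conditional form. The visible plan leaves the control image undefined, its labels point towards the eligibility photo, and combined visits put both on one occasion. If the eligibility photo is the control, the expected zero-effect rate is about 51% to 71% under the assumed reliabilities (0.6 to 0.95) and exclusion shares (10% to 69%), against 50% with an unselected photo. The upward direction rests on two further assumptions: grade 3 is the top of the scale, whose range is not visible, and the images vary between occasions.

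This is a limit on interpretation. It should not be read as a demonstrated type I error, because no test against chance is visible. Nor would it account for a result near the 96.4% reported for the earlier pivotal study, since even the most extreme setting gave about 76%. It matters mainly if the observed rate is modest. The change is a cheap improvement worth making.

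**What to change.** Add to the endpoint definition and the photography section:

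1. The before image, for both the independent panel and the participant survey, is the Visit 2 photograph taken before marking.
2. The dimple grade for eligibility is read only from the Visit 1 photograph and is not regraded on the Visit 2 control photograph. This is needed because Visit 2 also re-checks eligibility; regrading there would bring the selection back.
3. Where Visits 1 and 2 are combined, two photo sets are taken with the participant repositioned in between. Eligibility is graded on the first set and the second is the control. These participants are identified in the results.

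If redacted text already names the control image, check it against these three points.

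Cost: a few sentences, since the Visit 2 photographs are already scheduled, plus one extra photo set for each combined visit. For those participants the bias is only partly removed, because same-day repositioning does not capture day-to-day variation.
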